4.6.1.1. Other Clinically Relevant Information

Additional details concerning safety observations from clinical studies and for which a causal association has not been established or which are of minimal clinical significance may be found in the Investigator's Brochure. Please refer to Section 6: 'Summary of Data and Guidance for the Investigator'.

Adverse Events of Special Interest

Seizure

Three cases of seizures have occurred in the cabotegravir program cumulatively through 01 October 2015. Two of the cases occurred in HIV uninfected subjects with a prior history of seizure and one case involved a subject in study 200056 with circumstantial and anecdotal evidence of illicit drug use. Overall, there is not convincing evidence that cabotegravir exposure may be causally associated with seizure or with reduction of seizure threshold, due to the low frequency of reports, the confounders present in the cases received to date and lack of any pre-clinical signal or identified plausible mechanism. However seizure and seizure-like events are considered as AEs of special interest for close monitoring in all studies. Subjects with recent history of, or recent treatment for seizure will be excluded from study participation.

4.6.2. Benefit Assessment

Subjects participating in this study may not receive any clinical benefit, but will be compensated for their time and participation.

Benefit considerations may include:

- Contributing to the process of developing new therapies for HIV treatment and prevention that are not critically dependent upon adherence to daily dosing.
- Medical evaluations and assessments associated with study procedures (e.g. physical exam, ECG, laboratory studies, etc.).

4.6.3. Overall Benefit:Risk Conclusion

Review of the cumulative safety data on CAB oral and LA has not identified any safety signals which are considered to pose an unacceptable risk to healthy volunteers. Considering the multiple and overlapping measures that will be taken to minimize risk to subjects participating in this study, the potential risks identified in association with CAB are justified by the anticipated benefits that may be afforded to subjects including close medical monitoring and satisfaction of contributing to the ongoing continued clinical development of CAB for both the treatment and prevention of HIV infection.

5. SELECTION OF STUDY POPULATION AND WITHDRAWAL CRITERIA

Deviations from inclusion and exclusion criteria are not allowed because they can potentially jeopardize the scientific integrity of the study, regulatory acceptability or subject safety. Therefore, adherence to the criteria as specified in the protocol is essential.

5.1. Inclusion Criteria

This study does not involve a randomization procedure, as all subjects will receive the same dose of the same product.

Specific information regarding warnings, precautions, contraindications, adverse events, and other pertinent information on the ViiV Healthcare investigational product or other study treatment that may impact subject eligibility is provided in the Investigator's Brochure.

A subject will be eligible for inclusion in this study only if all of the following criteria apply:

AGE
1. Between 18 and 55 years of age inclusive, at the time of signing the informed consent.

TYPE OF SUBJECT AND DIAGNOSIS INCLUDING DISEASE SEVERITY
2. Healthy as determined by the investigator or medically qualified designee based on a medical evaluation including medical history, physical examination, laboratory tests and cardiac monitoring.
3. A subject with a clinical abnormality or laboratory parameter(s) which is/are not specifically listed in the inclusion or exclusion criteria, outside the reference range for the population being studied may be included only if the investigator in consultation with the Medical Monitor agree and document that the finding is unlikely to introduce additional risk factors and will not interfere with the study procedures. A single repeat of a procedure or lab parameter is allowed to determine eligibility.

WEIGHT
4. Body weight \geq 40 kg and body mass index (BMI) within the range 18.5 to 35 kg/m ² (inclusive).

SEX
5. Male or female

6. A female subject is eligible to participate if she is pre-menopausal, has an intact uterus and cervix, AND is not pregnant (as confirmed by a negative human chorionic gonadotrophin (hCG) test), not lactating, and at least one of the following conditions applies:
- a. Non-reproductive potential defined as:
 - Pre-menopausal females with one of the following:
 - Documented tubal ligation
 - Documented hysteroscopic tubal occlusion procedure with follow-up confirmation of bilateral tubal occlusion
 - Documented Bilateral Oophorectomy
 - b. Reproductive potential and agrees to follow one of the options listed below in the GSK Modified List of Highly Effective Methods for Avoiding Pregnancy in Females of Reproductive Potential (FRP) requirements from 30 days prior to the first dose of study medication and until at least five terminal half-lives OR until any continuing pharmacologic effect has ended, whichever is longer (can be up to 66 weeks on study) after the last dose of study medication and completion of the follow-up visit.

GSK Modified List of Highly Effective Methods for Avoiding Pregnancy in Females of Reproductive Potential (FRP) This list does not apply to FRP with same sex partners, when this is their preferred and usual lifestyle or for subjects who are and will continue to be abstinent from penile-vaginal intercourse on a long term and persistent basis.

- Contraceptive subdermal implant that meets the SOP effectiveness criteria including a <1% rate of failure per year, as stated in the product label
- Intrauterine device or intrauterine system that meets the SOP effectiveness criteria including a <1% rate of failure per year, as stated in the product label [Hatcher, 2007a]
- Oral Contraceptive, either combined or progestogen alone [Hatcher, 2007a]
- Injectable progestogen [Hatcher, 2007a]
- Percutaneous contraceptive patches [Hatcher, 2007a]
- Male partner sterilization with documentation of azoospermia prior to the female subject's entry into the study, and this male is the sole partner for that subject [Hatcher, 2007a].

These allowed methods of contraception are only effective when used consistently, correctly and in accordance with the product label. The investigator is responsible for ensuring that subjects understand how to properly use these methods of contraception. Female subjects desiring pregnancy or foresee that they might wish to become pregnant within 52 weeks of receiving a CAB LA injection must be excluded.

All subjects participating in the study must be counseled on safe sexual practices including the use of effective barrier methods to minimize risk of HIV transmission.

INFORMED CONSENT

7. Capable of giving signed informed consent as described in Section 10.2, which includes compliance with the requirements and restrictions listed in the consent form and in this protocol.

5.2. Exclusion Criteria

A subject will not be eligible for inclusion in this study if any of the following criteria apply:

CONCURRENT CONDITIONS/MEDICAL HISTORY (INCLUDES LIVER FUNCTION AND QTc INTERVAL)

Liver Function:

1. ALT or AST > ULN
2. Total bilirubin >ULN (isolated total bilirubin >ULN is acceptable if total bilirubin is fractionated and direct bilirubin <35%).
3. Current or chronic history of liver disease, or known hepatic or biliary abnormalities (with the exception of Gilbert's syndrome or asymptomatic gallstones)

QTc Interval:

4. QTc > 450 msec

NOTES:

- The QTc is the QT interval corrected for heart rate according to Bazette's formula ($QTc(QTcF B)$), machine-read or manually over-read.
- QTcB will be used to determine eligibility for an individual subject.
- For purposes of data analysis, QTcB or a composite of available values of QTc will be used as specified in the Reporting and Analysis Plan (RAP).
- Exclusion criteria for screening ECG (a single repeat is allowed for eligibility determination):

	Males	Females
Heart rate	<45 and >100 bpm	<50 and >100 bpm
QRS duration	>120 msec	
QTc interval	>450 msec	

5. The subject's systolic blood pressure is outside the range of 90-140mmHg, or diastolic blood pressure is outside the range of 45-90mmHg.
6. History of clinically significant cardiovascular disease including:
 - Evidence of previous myocardial infarction (pathologic Q waves, S-T segment changes (except early repolarization)).
 - History/evidence of symptomatic arrhythmia, angina/ischemia, coronary

artery bypass grafting (CABG) surgery or percutaneous transluminal coronary angioplasty (PCTA) or any clinically significant cardiac disease.

- Any conduction abnormality (including but not specific to left or right complete bundle branch block, AV block [2nd degree (type II) or higher], Wolf Parkinson White [WPW] syndrome).
 - Sinus pauses > 3 seconds.
7. Any significant arrhythmia which, in the opinion of the principal Investigator and GSK Medical Monitor, will interfere with the safety for the individual subject. Non-sustained (≥ 3 consecutive ventricular ectopic beats) or sustained ventricular tachycardia.
 8. History of ongoing or clinically relevant seizure disorder within the previous 2 years, including subjects who have required treatment for seizures within this time period. A prior history of seizure, with a seizure free period of at least 2 years, off anti-epileptics, may be considered for enrolment if the investigator believes the risk of seizure recurrence is low. All cases of prior seizure history should be discussed with the medical monitor prior to enrolment.

CONCOMITANT MEDICATIONS

9. The use of any concurrent prohibited medications as outlined in Section [6.10.2](#)

RELEVANT HABITS

10. History of regular alcohol consumption within 6 months of the study defined as: An average weekly intake of >14 drinks for males or >7 drinks for females. One drink is equivalent to 12 g of alcohol: 12 ounces (360 ml) of beer, 5 ounces (150 ml) of wine or 1.5 ounces (45 ml) of 80 proof distilled spirits.
11. Inability or unwillingness to comply with lifestyle and/or dietary restrictions outlined in Section [6.9](#).
12. High-risk behavior for HIV infection which includes, but is not limited to one of the following risk factors within six months before entering the study (day 1 of the oral lead-in): Unprotected vaginal or anal sex with a known HIV-infected person or a casual partner, engaged in sex work for money or drugs, acquired a sexually transmitted disease, high risk partner currently or in the previous six months or intravenous drug use.

CONTRAINDICATIONS

13. History of sensitivity to any of the study medications, or components thereof or a history of drug or other allergy that, in the opinion of the investigator or Medical Monitor, contraindicates their participation.
14. For subjects participating in MRI imaging: Contraindication for MRI scanning (as assessed by local MRI safety questionnaire), which includes but is not limited to:
 - a. Intracranial aneurysm clips (except Sugita) or other non-MRI compatible metallic objects
 - b. Intra- orbital metal fragments that have not been removed by a medical professional
 - c. Pacemakers or other implanted cardiac rhythm management devices and non-MRI compatible heart valves
 - d. Inner ear implants
 - e. History of claustrophobia

DIAGNOSTIC ASSESSMENTS AND OTHER CRITERIA

15. Positive hepatitis B surface antigen, or a positive hepatitis B core antibody with negative hepatitis B surface antibody) test result at screening or within 3 months prior to first dose of study treatment.
16. Positive hepatitis C antibody test result at screening or within 3 months prior to first dose of study treatment
17. A positive pre-study drug/alcohol screen (specific drugs are listed in Section 7.4.6). A positive drug screen is permitted if due to a prescribed medication, provided that medication is not on the list of prohibited medications in Section 6.10.2 and approved by the investigator and medical monitor.
18. A positive test for HIV antibody.
19. A positive pre-study screen for sexually transmitted diseases including *Neisseria gonorrhoea* or *Chlamydia trachomatis*, Trichomonas, syphilis, or an active HSV genital lesion.
20. Presence of a tattoo or other dermatological condition overlying the buttocks which in the opinion of the investigator may interfere with the interpretation of injection site reactions.
21. The subject has participated in a clinical trial and has received an investigational product within the following time period prior to the first dosing day in the current study: 30 days, 5 half-lives or twice the duration of the biological effect of the investigational product (whichever is longer).
22. Exposure to more than four new chemical entities within 12 months prior to the first dosing day.

DIAGNOSTIC ASSESSMENTS AND OTHER CRITERIA

23. Where participation in the study would result in donation of blood or blood products in excess of 500 ml within a 56 day period.
24. Unwillingness or inability to follow the procedures outlined in the protocol.
25. Subject is mentally or legally incapacitated.

Additional Criteria for Female Subjects Only:

26. Any current medical conditions that in the opinion of the investigator may compromise the conduct or analysis of the genital tract sampling (e.g., active genital tract infection or lesions).
27. Inability to abstain from the use of intravaginal products (e.g. tampons, spermicides, lubricants, vaginal hygiene products, diaphragms) for 72 hours prior to the genital tract sample collection visits and for up to 72 hours after.
28. Inability to abstain from any sexual activity (e.g., vaginal intercourse, masturbation, and penetration of the vagina by penises, fingers, tampons, sex toys) for 72 hours prior to the genital tract sample collection visits and for up to 72 hours after.

Additional Criteria for Male Subjects and Female Subjects who consent to rectal PK sampling:

29. Any current medical conditions that in the opinion of the investigator may compromise the conduct or analysis of the rectal compartment sampling (e.g., active rectal compartment infection, lesions or disease).
30. Inability to abstain from the use of intrarectal products (e.g., suppositories, lubricants) for 72 hours prior to the rectal compartment sample collection visits and for up to 72 hours after.
31. Inability to abstain from any receptive anal sexual activity (e.g., anal receptive intercourse and penetration of the rectum by fingers, sex toys or other) for 72 hours prior to the rectal compartment sample collection visit and for up to 72 hours after.

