5.4. Withdrawal/Stopping Criteria

Subjects may voluntarily withdraw from the study at any time and for any reason. Site investigators and study staff may withdraw participants before their scheduled termination visit for safety, behavioral, or administrative reasons, or if the participants are unable or unwilling to comply with study procedures. The reasons for withdrawals will be recorded in the participants' study records. If a subject withdraws from the study, he/she may request destruction of any samples taken, and the investigator must document this in the site study records.

During the oral lead-in period, early withdrawal on medical grounds will occur if the participant develops a grade 3 or higher AE that is judged by the investigator to be related directly to the study product (see [Appendix 3](#) and [Appendix 4](#) for definitions and grading of severity of adverse events), or any AE that is deemed clinically significant by the investigator and is judged by the investigator to be related directly to the study product. For liver-related stopping criteria, please refer to [Section 5.4.1](#).

If a subject receives the IM injection of CAB LA, they will be followed 52-weeks post injection per protocol for appropriate procedures, including blood plasma PK sampling, and safety evaluations, and will not be removed from the study for medical reasons, unless they refuse to continue participation.

During the oral lead in phase additional pre-specified reasons for discontinuing a participant from the study (or, at minimum, discontinuing administration of study product and continuing safety evaluations) include:

- Pregnancy (please see [Section 7.4.2](#))
- Protocol deviation
- Non-compliance
- Subject withdraws consent
- Subject lost to follow-up
- Investigator discretion
- Sponsor discontinues study

The following actions must be taken in relation to a subject who fails to attend the clinic for a required study visit:

- The site must attempt to contact the subject and re-schedule the missed visit as soon as possible.
- The site must counsel the subject on the importance of maintaining the assigned visit schedule and ascertain whether or not the subject wishes to and/or should continue in the study.

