Alkaline Phosphatase, High	1.25 to < 2.5 x ULN	2.5 to < 5.0 x ULN	5.0 to < 10.0 x ULN	≥ 10.0 x ULN
Alkalosis	NA	pH > ULN to ≤ 7.5	pH > 7.5 without life- threatening consequences	pH > 7.5 with life- threatening consequences
ALT or SGPT, High Report only one	1.25 to < 2.5 x ULN	2.5 to < 5.0 x ULN	5.0 to < 10.0 x ULN	≥ 10.0 x ULN
Amylase (Pancreatic) or Amylase (Total), High Report only one	1.1 to < 1.5 x ULN	1.5 to < 3.0 x ULN	3.0 to < 5.0 x ULN	≥ 5.0 x ULN
AST or SGOT, High Report only one	1.25 to < 2.5 x ULN	2.5 to < 5.0 x ULN	5.0 to < 10.0 x ULN	≥ 10.0 x ULN
Bicarbonate, Low (mEq/L; mmol/L)	16.0 to < LLN 16.0 to < LLN	11.0 to < 16.0 11.0 to < 16.0	8.0 to < 11.0 8.0 to < 11.0	< 8.0 < 8.0
Bilirubin Direct Bilirubin¹⁴, High > 28 days of age	NA	NA	> ULN	> ULN with life- threatening consequences (e.g., signs and symptoms of liver failure)
≤ 28 days of age	ULN to ≤ 1 mg/dL	> 1 to ≤ 1.5 mg/dL	> 1.5 to ≤ 2 mg/dL	> 2 mg/dL

PARAMETER	GRADE 1 MILD	GRADE 2 MODERATE	GRADE 3 SEVERE	GRADE 4 POTENTIALLY LIFE-THREATENING
Total Bilirubin, High > 28 days of age	1.1 to < 1.6 x ULN	1.6 to < 2.6 x ULN	2.6 to < 5.0 x ULN	≥ 5.0 x ULN
≤ 28 days of age	Total Bilirubin for Term and Preterm Neonates	Total Bilirubin for Term and Preterm Neonates	Total Bilirubin for Term and Preterm Neonates	Total Bilirubin for Term and Preterm Neonates
Calcium, High (mg/dL; mmol/L) ≥ 7 days of age	10.6 to < 11.5 2.65 to < 2.88	11.5 to < 12.5 2.88 to < 3.13	12.5 to < 13.5 3.13 to < 3.38	≥ 13.5 ≥ 3.38
< 7 days of age	11.5 to < 12.4 2.88 to < 3.10	12.4 to < 12.9 3.10 to < 3.23	12.9 to < 13.5 3.23 to < 3.38	≥ 13.5 ≥ 3.38
Calcium (ionized), High (mg/dL; mmol/L)	> ULN to < 6.0 > ULN to < 1.5	6.0 to < 6.4 1.5 to < 1.6	6.4 to < 7.2 1.6 to < 1.8	≥ 7.2 ≥ 1.8
Calcium, Low (mg/dL; mmol/L) ≥ 7 days of age	7.8 to < 8.4 1.95 to < 2.10	7.0 to < 7.8 1.75 to < 1.95	6.1 to < 7.0 1.53 to < 1.75	< 6.1 < 1.53
< 7 days of age	6.5 to < 7.5 1.63 to < 1.88	6.0 to < 6.5 1.50 to < 1.63	5.50 to < 6.0 1.38 to < 1.50	< 5.50 < 1.38
Calcium (ionized), Low (mg/dL; mmol/L)	< LLN to 4.0 < LLN to 1.0	3.6 to < 4.0 0.9 to < 1.0	3.2 to < 3.6 0.8 to < 0.9	< 3.2 < 0.8
Cardiac Troponin I, High	NA	NA	NA	Levels consistent with myocardial infarction or unstable angina as defined by the local laboratory
Creatine Kinase, High	3 to < 6 x ULN	6 to < 10 x ULN	10 to < 20 x ULN	≥ 20 x ULN

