12.5. Appendix 5: Toxicity Management

ANEMIA

Grade 1 (mild) hemoglobin decrease:

Any hemoglobin decrease meeting the definition of Grade 1 must be repeated with the following additional tests:

- peripheral blood smear
- indirect bilirubin (abnormal if increased >50% from baseline)
- haptoglobin (abnormal if ≤ 25 mg/dL)
- reticulocyte count (abnormal if $\geq 4\%$)

If the additional tests are within the normal range, subjects may continue study medication. If one or more of the additional tests is abnormal or suggestive of hemolytic anemia as specified above, subjects will permanently discontinue study medication and be withdrawn from the trial. Subjects should be followed up until resolution of anemia.

Grade 2 (moderate) hemoglobin decrease:

Any hemoglobin decrease meeting the definition of Grade 2 must be repeated with the following additional tests:

- peripheral blood smear
- indirect bilirubin (abnormal if increased > 50% from baseline)
- haptoglobin (abnormal if ≤ 25 mg/dL)
- reticulocyte count (abnormal if $\geq 4\%$)

If the additional tests are within the normal range, subjects may continue study medication. If one or more of the additional tests is abnormal or suggestive of hemolytic anemia as specified above, subjects will permanently discontinue study medication and be withdrawn from the trial. Consultation with a Hematologist should be considered. Subjects should be followed up until resolution of anemia.

Grade 3 (severe) or Grade 4 (potentially life threatening) hemoglobin decrease:

Any hemoglobin decrease meeting the definition of Grade 3 or 4 must be repeated with the following additional tests:

- peripheral blood smear
- indirect bilirubin
- haptoglobin
- reticulocyte count

Subjects will permanently discontinue study medication and be withdrawn from the trial. Consultation with a Hematologist should be considered. Subjects should be followed up until resolution of anemia.

TOTAL BILIRUBIN ELEVATION

Grade 1 (mild) bilirubin elevation (1.1 - 1.5 times ULN) or Grade 2 (moderate - 1.6-2.5 times ULN):

Any bilirubin value above the upper limit of normal must be repeated and fractionated (direct and indirect bilirubin). Subjects may continue study medication. Subjects should be followed up until resolution (return to baseline) of elevation.

Grade 3 (severe – 2.6-5.0 times ULN) or 4 (life-threatening - > 5.0 times ULN) bilirubin elevation:

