Any bilirubin value above the upper limit of normal must be repeated and fractionated (direct and indirect bilirubin). Subjects will permanently discontinue study medication and be withdrawn from the trial. Subjects should be followed up until resolution (return to baseline) of bilirubin elevation.

AST AND ALT ELEVATION

See [Appendix 2](#).

RASH

Grade 1 rash (Localized macular rash):

Subjects with Grade 1 rash should be evaluated by the Investigator immediately. A dermatologist may be consulted and a biopsy may be obtained if recommended by the dermatologist. The study drug should be permanently discontinued if the following signs or symptoms are noted at any time:

- Temperature > 38.5°C
- Lymphadenopathy
- Pharyngitis
- Any indication of internal organ involvement (hepatitis, nephritis)

In the absence of the above signs or symptoms, subjects with Grade 1 rash may continue the study drug at the discretion of the Investigator. The subject should be advised to contact the Investigator immediately if there is any worsening of the rash, if any systemic signs or symptoms worsen, or if mucosal ulceration develops. If the rash is considered to be most likely due to concomitant illness or non-study medication, standard management, including discontinuation of the likely causative agent, should be undertaken. If no other causative factor is found after clinical evaluation, the subject may be treated symptomatically until the rash resolves. Antihistamines, topical corticosteroids or antipruritic agents may be prescribed. The subject should remain on the study to be followed for safety and PK as outlined in the Time and Events table.

Grade 2 rash (Diffuse macular, maculopapular, or morbilliform rash OR Target lesions):

Subjects with Grade 2 rash should be evaluated by the Investigator immediately. Digital photographs should be obtained. A dermatologist may be consulted and a biopsy may be obtained if recommended by the dermatologist. The study drug should be permanently discontinued if the following signs or symptoms are noted at any time:

- Temperature > 38.5°C
- Lymphadenopathy
- Pharyngitis
- Any indication of internal organ involvement (hepatitis, nephritis)

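### Exclusion criterion 2 accepts an isolated, mainly indirect bilirubin elevation with no upper limit, while Appendix 5 makes the same value a mandatory withdrawal from 2.6 x ULN

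*Protocol*

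**What the plan says.** **Entry.** Protocol Section 5.2, criterion 2, excludes total bilirubin above ULN with one exception: "isolated total bilirubin >ULN is acceptable if total bilirubin is fractionated and direct bilirubin <35" per cent. No upper limit on total bilirubin goes with the exception. Criterion 3 excludes liver disease and biliary abnormalities, "with the exception of Gilbert's syndrome or asymptomatic gallstones". Criterion 1 excludes raised ALT or AST.

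**On study.** Appendix 5 (Section 12.5) has a block headed "TOTAL BILIRUBIN ELEVATION", with bands set on total bilirubin:

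- For "Grade 1 (mild) bilirubin elevation (1.1 - 1.5 times ULN) or Grade 2 (moderate - 1.6-2.5 times ULN"), the value is repeated and fractionated and the subject may stay on drug.
- For "Grade 3 (severe – 2.6-5.0 times ULN) or 4 (life-threatening - > 5.0 times ULN) bilirubin elevation", the value is again repeated and fractionated, and then "Subjects will permanently discontinue study medication and be withdrawn from the trial".

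In both bands baseline appears only as the point to which the elevation is followed up.

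**The concern.** The entry rule looks at the direct fraction and accepts a mainly indirect elevation of any size. The stopping rule looks at total bilirubin alone. Appendix 5 asks for the fraction at the higher band but gives it no part in the action, and the threshold is not set against the subject's own starting value. One stable, isolated elevation can therefore be acceptable at screening and require withdrawal once on study.

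Such a subject would take oral drug, be withdrawn for the condition accepted at entry, and never reach the injection. The primary endpoints are all post-injection concentrations, so that subject would contribute none of them. Section 7.3 also bars re-screening after an enrolled subject is withdrawn.

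**Working it through.** There is no planned figure to reproduce; Section 9.2.1 says no formal sample size calculation was made. The check applies the two written rules to the same values.

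**Inputs.** T is total bilirubin in multiples of ULN and f is the direct fraction.

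- Entry (Section 5.2, criterion 2): eligible on bilirubin if T ≤ 1, or if the elevation is isolated and f < 35%.
- Appendix 5: T from 1.1 to 2.5, may continue; T of 2.6 or more, discontinue and withdraw.

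**Step 1: both rules on the same values.**

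| T | f | Criterion 2 | Appendix 5 |
|---|---|---|---|
| 1.3 | 30% | eligible | Grade 1, may continue |
| 2.0 | 20% | eligible | Grade 2, may continue |
| 2.5 | 34% | eligible | Grade 2, may continue |
| 2.6 | 10% | eligible | Grade 3, withdraw |
| 3.0 | 34% | eligible | Grade 3, withdraw |
| 5.0 | 30% | eligible | Grade 3, withdraw |

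The overlap is the whole region T ≥ 2.6 with f < 35%. Below it, from 1.1 to 2.5 x ULN, the two rules agree. As an illustration, assume a ULN of 1.2 mg/dL for total bilirubin (the documents give none). Total 3.2 with direct 0.5 mg/dL gives T = 3.2/1.2 = 2.67 and f = 0.5/3.2 = 15.6%, which is eligible and in the withdrawal band.

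**Step 2: does other text remove the overlap?**

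- Inclusion criterion 3 lets the investigator and Medical Monitor agree to accept an out-of-range value, but only for parameters not specifically listed. Bilirubin is listed.
- Inclusion criterion 2 requires the investigator to judge the subject healthy. That could keep such a subject out, but it is a judgement and not a limit.
- Section 5 allows no deviation from the entry criteria, and Section 7 allows no waiver except for immediate safety concerns.
- Section 7.3 has eligibility confirmed on Day 1 and again before injection. On bilirubin, that applies the same criterion and returns the same answer.

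None of these sets a numeric limit on total bilirubin or an exception to the Appendix 5 action.

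**Step 3: reach.** Let p be the share of enrolled subjects with T ≥ 2.6 and f < 35%. The documents do not give p, so a range is assumed. With about 20 enrolled, P(at least one) = 1 − (1 − p)^20.

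| p (assumed) | P(at least one in 20) |
|---|---|
| 0.1% | 1 − 0.999^20 = 2% |
| 0.5% | 1 − 0.995^20 = 9.5% |
| 1% | 1 − 0.99^20 = 18% |
| 2% | 1 − 0.98^20 = 33% |

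**The case against.** The best defence is that an on-treatment stopping threshold need not match an entry threshold, and that a stable elevation at this level would be seen in time. Section 7.3 requires all screening results before enrolment, and the investigator must judge the subject healthy on laboratory tests, among other things. Appendix 5 also calls for a repeat, so one stray value is not the whole basis for action. About 20 subjects are enrolled to yield 16 evaluable, and Section 4.3 allows replacements.

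Much of this stands, and it limits the size of the point. The Section 7.1.1 footnote lets dosing start before Day 1 chemistry is back, but that adds little when screening has already shown the value. What the defence does not supply is a rule. A site that sees 2.7 x ULN at screening, mainly indirect, is told by criterion 2 that the subject qualifies and by Appendix 5 that the same value requires withdrawal. Repeating a stable value only confirms it. The two thresholds may differ for good reasons, but the plan does not say how a subject accepted under the exception is to be handled.

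A reader might also see a third conflicting rule in Appendix 4, where the adult row "Direct Bilirubin¹⁴, High" makes any value above ULN Grade 3. The documents do not support that. Section 7.4.1 uses Appendix 4 to grade severity, and its total bilirubin row has essentially the same cut-offs as Appendix 5. Under Section 5.4 the grade leads to withdrawal only in the oral lead-in, and only if the subject "develops a grade 3 or higher AE that is judged by the investigator to be related directly to the study product". Section 4.4 is looser on relatedness but still requires an AE. Under Section 12.3.1 an abnormal laboratory result is an AE when the investigator considers it clinically significant, and Section 5.4 already withdraws for any clinically significant related AE, whatever its grade. The direct-bilirubin grade therefore adds no separate contradiction.

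**Conclusion.** The point holds in a narrow form. Criterion 2 and the Appendix 5 action for Grade 3 and 4 bilirubin contradict each other for total bilirubin of 2.6 x ULN or more with a direct fraction below 35%, and nothing else in the protocol resolves it.

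The reach is small and probably uncommon. The 2% to 33% range rests entirely on the assumed shares, and the investigator's judgement of health could lower them further. It would be tempting to infer a fixed loss from the evaluable sample, but over-enrolment and replacement mean the documents do not support one. It would also go too far to say that Appendix 5 ignores baseline: baseline is the endpoint of follow-up and is absent only from the action threshold. What remains is avoidable exposure of a subject who cannot then contribute to the primary endpoints, and an instruction that sites cannot apply consistently. No view is taken on which clinical rule is right.

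**What to change.** Reconcile Section 5.2, criterion 2, with the Appendix 5 action for Grade 3 and 4 total bilirubin, so that the same isolated, mainly indirect elevation is not both accepted at entry and a mandatory withdrawal on study. The medical monitor decides which passage changes and sets any threshold. The cost is a wording edit to one or both passages. Total and direct bilirubin are already in the clinical chemistry panel in Table 5, so no sample, visit or analysis is added.
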